8.1 Schedule of Events

The time and events table for the conduct of this study is shown below:

Table 1:

| Study Phase | Screening | | Injection | | Follow Up | | |
|---------------------------------|-----------------------------|-----------|------------------|-----------------------------|------------------------------|-------------------------------|---|
| | V1 | V2 | V3 | V4 | V5 | V6 | |
| Time Point | V1 | V2 | V3 | V4 | V5 | V6 | |
| Visit Window | 0 - 28days prior to therapy | Day 0 | Day 28 ± 7 | Week 4 Day 30 ± 7 | Week 12 Day 90 ± 7 | Week 24 Day 180 ± 7 | |
| Informed Consent | X | | | | | | |
| Demographics | X | | | | | | |
| Medical History | X | | | | | | |
| Physical Exam | X | | | | | | |
| Doppler Ultrasound | X | | | | | | X |
| Concomitant Medications/Therapy | X | X | X | X | X | | X |
| Review Adverse Events | | X | X | X | X | | X |
| Randomization | | X | | | | | |
| Study Therapy Injection | | X | X | | | | |
| Questionnaires | IIEF | X | | X | X | | X |
| | SEP3 | X | | X | X | | X |
| | EDITS | | | X | X | | X |
| | VAS | | X | X | | | |
| Laboratory Testing | Hematology | X | | | | | |
| | Chemistry | X | | | | | |
| | HbA1c | X | | | | | |
| | Testosterone | X | | | | | |

8.2 Description of Study Procedures

8.2.1 *Informed Consent:* Refer to Section 7.3 for details regarding the informed consent process. Study procedures will be completed only after participants have signed the informed consent documentation.

8.2.2 *Demographics:* Demographic characteristics will be recorded including: date of birth, gender, marital status, race and ethnicity. If Medical history has been recorded as part of their participation in another study those source documents may be requested and used for the purpose of this research study.

8.2.3 *Medical History:* Assessment of current and past medical, surgical, and social history will be conducted.

8.2.4 *Physical Examination:* Genitourinary/Reproductive system physical exam will be performed.

8.2.5 *Doppler Ultrasound:* Penile Doppler ultrasound will be performed as standard of care for the management of erectile dysfunction. Results from within the past 12 months can be extracted from the medical record for use in this study.

8.2.6 *Concomitant Medications:* Review of current use of prescription and over the counter (OTC) medications. Participants must discontinue use of PDE5i medications throughout the duration of the study.

8.2.7 *Review Adverse Events:* Refer to Section 12 for description and reporting of adverse and serious adverse events

8.2.8 *Randomization:* Refer to Section 9.3 for details about randomization plan

8.2.9 *Study Therapy Injection:* Approximately 120mL of blood will be collected from participants for preparation of investigational product. Refer to Section 9.2 for description of IP preparation and administration.

8.2.10 *International Index of Erectile Function (IIEF) Questionnaire:* This validated 15-item self-evaluation scale provides pre and post treatment clinic evaluations of erectile function, orgasmic function, sexual desire, satisfaction in sexual intercourse and general satisfaction. If the subject has completed the IIEF questionnaire within the past 6 months, those results may be requested and used for the purpose of this research study. Questionnaires will be completed prior to therapy at injection visits.

8.2.11 *Sexual Encounter Profile (SEP3) Questionnaire:* This 5-item questionnaire is completed after each sexual intercourse attempt. Participants will be asked to complete the short version consisting of question #2 and #3 only.

8.2.12 *Erectile Dysfunction Inventory of Treatment Satisfaction (EDITS) Questionnaire:* This is a psychometrically sound questionnaire used to assess satisfaction with medical treatment modalities for erectile dysfunction.

8.2.13 *Visual Analogue Pain Scale (VAS):* The visual analog scale (VAS) is a validated, subjective measure for acute and chronic pain. Scores are recorded by making a handwritten mark on a line that represents a continuum between “no pain” and “worst pain”.

8.2.14 *Laboratory Testing:* Hematology, chemistry, hemoglobin A1C, and serum testosterone, lab test results will be recorded at screening. If any standard of care labs tests have been performed within 12 months of visit date, those results may be used for the purpose of this study.

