- The percentage of subjects in each group who attain MCID in IIEF-EF domain from baseline to 12 & 24 weeks after final treatment.
- The difference between groups in change of IIEF-EF score from baseline to 4, 12, & 24 weeks after final treatment.

- Differences in Doppler ultrasound parameters (PSV and EDV) from baseline to 24 weeks after final treatment.

4.3 Secondary Endpoints (safety):

- Incidence of adverse events in all patients during the study period. Anticipated adverse events that will be recorded at every visit are the following
 - o Pain
 - o Bruising
 - o Swelling
 - o Edema
 - o Allergy
 - o Penile Fracture
 - o New Penile Curvature

4.4 Exploratory Endpoints:

- Change in stretched penile length from baseline to 24 weeks after final treatment.
- The percentage of subjects in each group who attain MCID in IIEF-EF domain from baseline to 4 weeks after final treatment.

5. Study Location

The study will be funded by the Department of Urology and coordinated by the University of Miami (UM), Miller School of Medicine, Department of Urology. The UM Interdisciplinary Stem Cell Institute (ISCI) will also support the project (logistics, quality control, management, storage of specimens and data). All study visits will be carried out in the Department of Urology clinics, (ADDRESS: [name], University of Miami Miller School of medicine, Miami, FL. & Lennar address) PRP preparation will take place in the clinic's andrology lab.

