8.3 Description of Study Visits

8.3.1 Visit 1: Screening Visit

Visit 1 (0 – 28 days before therapy): The basic work-up will take place, including medical and sexual history, as well as necessary lab tests (testosterone, prolactin, hematology, chemistry), if not available during the last 12 months prior to screening. Subjects will complete the IIEF-ED questionnaire. We will ensure that patients have 4 attempts for intercourse, which they will record on the SEP diaries. PDE5i use is prohibited throughout the study. Screening visit can occur on same day as first injection. Refer to table 1 for procedures to be performed at the Screening visit.

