8.3.2 Visit 2-3: Injection Visits (Day 0 & Day 28)

All participants will complete the IIEF questionnaire, and SEP diaries will be evaluated. Upon evaluation of eligibility, subjects will be randomized to one of the 2 parallel study groups, using an online program, and initiate treatment on the same day.

There will be 2 treatment visits for all Groups with 28 ± 7 days treatment interval for all subjects. Subjects will complete a Visual Analogue Scale (VAS) pain score after the end of each treatment. Refer to table 1 for all procedures to be performed at the Intervention Visits.

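### A record Doppler scan up to 12 months old may serve as baseline for the PSV/EDV change endpoint, and the planned analysis adjusts for neither baseline value nor scan age

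*Combined protocol and SAP*

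**What the plan says.** The synopsis and section 4.2 list as a secondary efficacy endpoint "Differences in Doppler ultrasound parameters (PSV and EDV) from baseline to 24 weeks after final treatment". The "Doppler Ultrasound" row of Table 1 (section 8.1) marks only V1 and V6, so the endpoint rests on two scans.

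Section 8.2.5 describes how they are obtained: "Penile Doppler ultrasound will be performed as standard of care for the management of erectile dysfunction". It then adds: "Results from within the past 12 months can be extracted from the medical record for use in this study". It does not say from which date the 12 months are counted, or whether the allowance covers baseline only. By contrast, section 8.2.14 counts its similar allowance for laboratory tests from the visit date.

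The protocol does not ask for the scan date, set a shorter limit on scan age for this endpoint, or fix how the scan is acquired. Section 13.1 analyses continuous data by repeated-measures ANOVA or a t-test between groups, with no adjustment for baseline value or scan age.

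**The concern.** The endpoint is defined as change over one period, but two men in the same arm may have baseline scans taken about a year apart relative to treatment. An older scan, taken in routine care, may track the V6 value less closely than one taken at screening. If so, subtracting it adds noise to the change score, and a real difference in PSV or EDV is harder to see.

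At stake is the precision of one secondary comparison. The primary IIEF-EF responder analysis does not use the Doppler data.

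**Working it through.** The documents give no SD, effect size or power for PSV or EDV, so there is no stated figure to reproduce.

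**Interval from baseline scan to V6**

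Inputs:
- V1: "0 - 28days prior to therapy" (Table 1). Its lower end is confirmed by "Screening visit can occur on same day as first injection" (section 8.3.1).
- First to second injection: "There will be 2 treatment visits for all Groups with 28 ± 7 days treatment interval for all subjects" (section 8.3.2). The synopsis and section 8 give 30 ± 7 days.
- Second injection to V6: Day 180 ± 7 (Table 1), counted from the final injection.
- Record scan: up to 12 months, taken as 365 days (section 8.2.5).

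Interval = age of record scan + V1 to Day 0 + Day 0 to second injection + second injection to V6. Months are days / 30.44.

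| Baseline scan | Days | Months |
|---|---|---|
| At V1, V1 on Day 0 | 0 + 28 + 180 = 208 | 6.8 |
| At V1, V1 28 days before Day 0 | 28 + 28 + 180 = 236 | 7.8 |
| Record scan 365 days before Day 0 | 365 + 28 + 180 = 573 | 18.8 |
| Record scan 365 days before a V1 held 28 days before Day 0 | 365 + 28 + 28 + 180 = 601 | 19.7 |

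The last row assumes that the 12 months count back from V1. With visit windows at their limits, the extremes are 21 + 173 = 194 days and 365 + 28 + 37 + 187 = 617 days. Reading week 24 as day 168 gives 28 + 168 = 196 to 365 + 28 + 28 + 168 = 589 days. The 28- and 30-day injection intervals, and week 24 and day 180, need reconciling in the protocol, but neither changes the picture here.

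**Precision of the planned analysis**

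With two time points, the group-by-time test of a repeated-measures ANOVA is the t-test on change. In units of the common variance, and with equal SDs at both times:

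- Variance of change = 2(1 − r), where r is the correlation between the two scans.
- If a share s of the men have old scans: variance = (1 − s) × 2(1 − r_new) + s × 2(1 − r_old).

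All correlations and shares below are assumptions. Power is for 32 men per arm (40 less 20% attrition), two-sided 0.05, with the effect set to give 80% when all scans are from screening.

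| r_new | r_old | Share old | Variance of change | Rise | Power |
|---|---|---|---|---|---|
| 0.7 | 0.4 | 1/4 | 0.75 × 0.60 + 0.25 × 1.20 = 0.75 (from 0.60) | 25% | 71% |
| 0.7 | 0.4 | 1/2 | 0.5 × 0.60 + 0.5 × 1.20 = 0.90 (from 0.60) | 50% | 63% |
| 0.7 | 0.4 | all | 1.20 (from 0.60) | 100% | 51% |
| 0.7 | 0.5 | 1/2 | 0.5 × 0.60 + 0.5 × 1.00 = 0.80 (from 0.60) | 33% | 68% |
| 0.5 | 0.4 | 1/2 | 0.5 × 1.00 + 0.5 × 1.20 = 1.10 (from 1.00) | 10% | 76% |
| any | unchanged | any | unchanged | 0% | 80% |

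Below r = 0.5, 2(1 − r) exceeds 1, so the change score is noisier than the week-24 value alone.

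**What ANCOVA on baseline recovers**

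For men sharing one correlation, the error variance is 1 − r². Relative to the change score it is (1 − r²) / [2(1 − r)] = (1 + r)/2.

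- r = 0.7: 0.51 against 0.60, ratio 0.85, so 15% lower.
- r = 0.4: 0.84 against 1.20, ratio 0.70, so 30% lower.

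If all men have old scans at r = 0.4, ANCOVA leaves 0.84. That is better than 1.20, but above the 0.60 of an unadjusted change score at r = 0.7. Scan age as an additive covariate removes average drift with scan age. It does not restore a weaker correlation.

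**The case against.** The strongest reply is that little is at risk. The trial is labelled Phase I and pilot, the endpoint is secondary and unpowered, and section 13.1 plans only comparisons between arms. Scan age is settled before randomisation on Day 0 (section 9.3), so it cannot favour either arm except by chance. How many men will use a record scan is unknown, as are the correlations. All of this stands, and it limits the point to a possible loss of precision.

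Three stronger readings are tempting, and the documents do not support them.

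- **PDE5i withdrawal distorts the change.** Section 6 describes the men as regular PDE5i users, and section 8.3.1 says "PDE5i use is prohibited throughout the study", so a reader might infer that an old scan reflects a drug effect that V6 does not. This is possible, but no section says that PDE5i use alters PSV or EDV. A V1 scan might itself precede the end of the one-month wash-out, since nothing requires it to come after.
- **A fresh V1 scan must be required.** Table 1 schedules one, but section 8.2.5 lets a record result fill that slot. Requiring the scan would add a procedure for those men.
- **Doppler is the only objective measure of efficacy.** Section 4.4 also lists stretched penile length, as an exploratory endpoint.

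One part of the reply needs a condition. The argument that scan age cannot bias the comparison holds only if record scans are confined to baseline, and section 8.2.5 does not say so.

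**Conclusion.** The point holds as a modest, correctable weakness in one secondary endpoint. The interval range, about 7 months to about 19-20 months, follows from the protocol's own windows. Its top end depends on an anchor date that the protocol does not give.

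The loss of precision is conditional. It runs from none, if the correlation does not fall with scan age, through 10% more variance in a mild case, to 100% more if the correlation falls from 0.7 to 0.4 and every man uses an old scan. A reader might take that doubling as the expected loss. It is the least favourable of the cases shown and rests wholly on assumed figures.

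A reader might also infer bias between the arms. With record scans confined to baseline, none is expected, although chance imbalance in scan age is possible with 40 men per arm.

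**What to change.** - **Section 8.2.5:** state that record scans may serve as the baseline only, state the date from which the 12 months are counted, and record the date of every scan used.
- **Section 13.1:** compare week-24 PSV and EDV between arms by ANCOVA, with the baseline value and scan age (days from scan to Day 0) as covariates, in place of the t-test or repeated-measures ANOVA for this endpoint.
- **Sensitivity analysis:** repeat the comparison in men whose baseline scan falls in the 28-day screening window. Report how many this retains, which may be few.

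The cost is a few sentences in the protocol and a scan-date field in the case report form, with no added scan or visit. ANCOVA improves on the change score at either correlation shown, but does not fully recover the precision lost to a weaker baseline correlation.

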8.3 Description of Study Visits

8.3.1 Visit 1: Screening Visit

Visit 1 (0 – 28 days before therapy): The basic work-up will take place, including medical and sexual history, as well as necessary lab tests (testosterone, prolactin, hematology, chemistry), if not available during the last 12 months prior to screening. Subjects will complete the IIEF-ED questionnaire. We will ensure that patients have 4 attempts for intercourse, which they will record on the SEP diaries. PDE5i use is prohibited throughout the study. Screening visit can occur on same day as first injection. Refer to table 1 for procedures to be performed at the Screening visit.

8.3.2 Visit 2-3: Injection Visits (Day 0 & Day 28)

All participants will complete the IIEF questionnaire, and SEP diaries will be evaluated. Upon evaluation of eligibility, subjects will be randomized to one of the 2 parallel study groups, using an online program, and initiate treatment on the same day.

There will be 2 treatment visits for all Groups with 28 ± 7 days treatment interval for all subjects. Subjects will complete a Visual Analogue Scale (VAS) pain score after the end of each treatment. Refer to table 1 for all procedures to be performed at the Intervention Visits.

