8.3.3 Visit 4-6: Follow Up Visits (Week 4, 12, 24) Post-Injection

Follow up visits will occur within 30 ± 7 days of final injection (V3). Refer to table 1 for procedures to be performed at the follow up visits visit.

9. Investigational Product

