9.2 Administration of IP

The patient will be positioned supine. A sterile field will be developed with Betadine prep of the genitalia, sterile gloves and a sterile extremity drape. A total of 20 ml of 1% lidocaine will be drawn up using an 18-gauge needle and will be subcutaneously administered using a 27-gauge needle into the subcutaneous tissue at the base of the penis to obtain a dorsal nerve block. A 1/4-inch Penrose drain will be used as a tourniquet by placing it at the base of the penis and maintaining it in place under tension by a sterile clamp. A maximum of 5mL of PRP will be infused steadily over a two-minute period – approximately 2.5 ml each into the right and left corpus cavernosum. The infusion will be performed at this slow speed (each side over 2 minutes of infusion) to minimize injury to

the platelet cells. In the control arm, men will be administered injectable normal saline that will be injected in a similar manner as the PRP.

Following administration of PRP or normal saline, compression of the penis will be achieved with a clenched fist for 20 minutes. At 20 minutes, the tourniquet will be removed, and a compressive dressing will be placed around the penile shaft. The patient will be instructed to remove the compression bandage in 4 hours and to contact the study coordinators if he experiences any problems.

Figure 1: Diagram of PRP Injection

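### No pain, bruising or swelling assessment is scheduled between the injection session, where the VAS is probably taken under nerve block, and a visit three to five weeks later

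*Combined protocol and SAP*

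**What the plan says.** **The endpoint.** The secondary safety endpoint is the incidence of adverse events (synopsis and Section 4.3). Section 4.3 adds "Anticipated adverse events that will be recorded at every visit are the following", and pain, bruising, swelling and edema are the first four items. The VAS is not named as a primary, secondary or exploratory endpoint.

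**The pain score.** Section 8.3.2: "Subjects will complete a Visual Analogue Scale (VAS) pain score after the end of each treatment". Section 8.2.13 describes the scale but gives no clock time and no recall period. The schedule of events carries two VAS marks, which fit the two injection visits (V2 and V3). The table's columns are broken in the text available, but no mark appears to belong to a follow-up visit.

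**The session.** Section 9.2: "A total of 20 ml of 1% lidocaine will be drawn up using an 18-gauge needle" and is given "into the subcutaneous tissue at the base of the penis to obtain a dorsal nerve block". The infusion follows. Then "compression of the penis will be achieved with a clenched fist for 20 minutes", and "At 20 minutes, the tourniquet will be removed". A compressive dressing is applied, which the man takes off himself four hours later. Saline is given in a similar manner, so I read the block and compression as common to both arms.

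**What comes next.** Section 8.3.2: "There will be 2 treatment visits for all Groups with 28 ± 7 days treatment interval for all subjects". The first follow-up (V4) is 30 ± 7 days after the second injection (Section 8.3.3 and the schedule). Adverse events are reviewed at every visit from V2 onwards. Between visits, the only route is Section 9.2's instruction to contact the coordinators about any problem.

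**The concern.** Soreness, bruising and swelling after a penile injection may appear and resolve within days. The plan has two ways of seeing them: a score taken at the session, and a question asked at a visit several weeks later. The first is probably taken while the area is numb. The second depends on a man remembering, and choosing to mention, something mild from about a month before.

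Safety is in the trial's title and is its secondary objective, and pain is the most frequent event in the prior data that the plan cites. If mild local events are missed at a similar rate in both arms, both incidences fall, the absolute difference between PRP and saline shrinks, and the trial is less able to detect extra local reactions from PRP. The reported frequencies, which readers would use to describe tolerability, would also be too low.

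**Working it through.** The plan states no figure on this point, so there is none to reproduce. The check concerns timing, followed by an illustration of direction.

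**1. When is the VAS taken relative to the block?** Inputs are from Section 9.2. The infusion is described both as taking two minutes and as taking two minutes per side, so 2 to 4 minutes. Compression lasts 20 minutes.
- If treatment ends at tourniquet removal: 2 + 20 = 22 to 4 + 20 = 24 minutes after the infusion starts.
- If treatment ends with the infusion: 2 to 4 minutes after it starts.

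The time from block to infusion is not stated, and neither is the delay from the end of treatment to the VAS. Assumption: the block lasts at least one hour and the VAS is taken promptly. The score then falls under the block on either reading. If the block were shorter, or the VAS were taken late, this step would weaken. Step 2 would not.

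**2. When is pain next asked about?**
- After injection 1: 28 − 7 = 21 to 28 + 7 = 35 days, or 3.0 to 5.0 weeks.
- After injection 2: 30 − 7 = 23 to 30 + 7 = 37 days, or 3.3 to 5.3 weeks.

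The synopsis and Section 8 give the treatment interval as 30 ± 7 days, whereas Section 8.3.2 and the schedule give 28 ± 7. These passages must be reconciled, but either one leaves a gap of about three to five weeks.

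**3. Could same-day review fill the gap?** Adverse event review is marked at V2 and V3, but whether it comes before or after the injection is not stated. Even afterwards, the penis is in a dressing once the tourniquet is off, and the dressing comes off about four hours later, away from staff. The physical examination is marked at screening only.

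**4. How often might pain occur?** Section 12.1 pools four reports: 9 + 16 + 10 + 40 = 75 men, with pain in 4.
- 4/75 = 5.3% (exact 95% CI 1.5–13.1%).
- All four come from the 16-man study in the background table: 4/16 = 25.0% (7.3–52.4%).
- Applied to 40 PRP men: 40 × 5.3% = 2.1, and 40 × 25% = 10.

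This is a range for events that might occur, not a count of events that would be missed.

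**5. What would under-capture do?** Illustration only: observed rate = capture fraction × true rate, the same fraction in both arms, 40 men per arm, Fisher's exact test at two-sided 0.05 (Section 13.1). True rates and capture fractions are assumed.

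| Capture | 5% vs 25%: difference | Power | 10% vs 40%: difference | Power |
|---|---|---|---|---|
| 100% | 20 points | 65% | 30 points | 85% |
| 75% | 15 points | 44% | 22.5 points | 68% |
| 50% | 10 points | 20% | 15 points | 41% |
| 25% | 5 points | 2% | 7.5 points | 9% |

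The ratio of rates stays at 25/5 = 5 or 40/10 = 4 throughout. Equal under-capture shrinks the absolute difference, the event counts and the power, but not the ratio.

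**The case against.** - **The endpoint is adverse event incidence, not the VAS.** This stands. No between-arm comparison of the VAS is specified beyond the generic methods in Section 13.1. A low VAS does not by itself bias the endpoint, and for adverse event pain the problem is only a risk of under-reporting.
- **The plan already collects these events.** Section 12.1 records every urological or reproductive event whatever its grade, Section 14 promises systematic recording at each visit, and men are told to make contact about problems. This stands in part. It is planned collection and will catch the memorable events, but it is not prospective measurement in the days when mild ones occur.
- **The VAS may be timed correctly for its purpose.** Tied to each treatment and with no stated recall period, it could be a tolerability rating of the whole procedure. This is fair, and is a reason to keep the score and label it. It then says nothing about later pain.
- **The prior data do not show what is missed.** The cited reports give no onset time, so some of the earlier pain may have occurred on the injection day. The 25% comes from a calcium-activated preparation in a group that included Peyronie's disease. This stands, and the 2-to-10 range is context only.

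A reader might infer that the penis is certainly still anaesthetised when the score is made, or that a true PRP–saline difference in pain would be masked. The documents support neither: the VAS time and block duration are unstated, and later reviews in both blinded arms can still pick up pain.

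**Conclusion.** The point holds as a gap in assessment timing. Pain after the block wears off, and short-lived bruising or swelling, are never measured prospectively. These listed safety events rest on recall over 21–35 days after injection 1 and 23–37 days after injection 2, or on a call that the man initiates.

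Two consequences follow, with different certainty. VAS scores are probably too low in both arms, if the block outlasts the session and the score is taken promptly. The incidence of short-lived local events is at risk of under-reporting, which would shrink the absolute difference between arms if capture is similar in each. The documents give no capture fraction, so the loss cannot be computed; the table in the working shows direction only. It would go too far to say that the pain comparison is driven to zero, or that the plan sets out to call PRP painless.

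Severity is minor to moderate. The primary endpoint, the sample size and the efficacy analyses are unaffected.

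**What to change.** In Section 8.3.2 and the schedule of events:

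1. State the clock time of the existing VAS relative to the block or to tourniquet removal, and label it procedural pain.
2. Add a take-home VAS and a short bruising and swelling checklist at fixed times after each session, for example at dressing removal, the next day and one week. Keep it with the SEP diary that men already fill in, and collect it at V3 and V4.
3. In Sections 4.3 and 13.1, say that these entries support the between-arm comparison of pain, bruising and swelling within the adverse event incidence endpoint. Fix in advance how a diary entry becomes a recorded event, and apply the rule equally in both arms.

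The cost is one diary page per session and a few eCRF fields, with no extra visit, staff or procedure. The downside is some incomplete pages and probably a higher reported rate of mild events, which should be expected when the results are set beside the earlier studies.
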